The individual studies included in the review are summarized in Table 2. All four studies are randomized controlled trials and used the standard dose of 200 μ g/kg ivermectin and 400 mg albendazole [4, 6-8]. Against infections with *T. trichiura*, CRs ranging from 27.5-81.1%, ERR based on geometric mean ranging from 91.3-99.7%, and ERR based on arithmetic mean ranging from 85.6-97.5% were observed. CRs for *T. trichiura*

observed in Asian settings were higher than in African settings. One reason for this finding may be differences in the study design and quality (*e.g.* in terms of diagnostic approach used). Another possible reason recently highlighted is genetic diversity of *T. trichiura* strains and variation in susceptibility to anthelmintics and/or drug resistance [9-11]. Interestingly, the higher efficacy of ivermectin in combination with albendazole translated – at least in some settings – into lower prevalences even after one year [4, 12]. The efficacy of albendazole-ivermectin against *A. lumbricoides* was excellent (CRs >78% and ERRs >99.5%), while moderate CRs (50-66.7%) and high ERRs (>95.4%) were observed against hookworm.

Study	Setting	Cure rate in % (nneg/n)	Eggs per gram (pre/post)	Egg reduction rate in %
Ismail et al. 1999	Sri Lanka	81.1% (43/53)	1544.0/78.7 (unkwn)	94.9% (unkwn)
Belizario et al. 2003	Philippines	65.1% (97/149)	4948.1/122.5 (ar)	97.5% (ar)
			550.0/1.9 (geo)	99.7% (geo)
Knopp et al. 2010	Tanzania (Pemba)	37.9% (53/140)	127/11 (geo)	91.3% (geo)
Speich et al. 2015	Tanzania	27.5% (30/109)	1059/153 (ar)	85.6% (ar)
•	(Pemba)		489/27 (geo)	94.5% (geo)
All studies		49.4% (223/451)		

Table 2. Known efficacy of co-administered ALB-IVM^a against T. trichiura:

^aConsidered doses: albendazole=400 mg, ivermectin=200 µg/kg

ar=arithmetic mean, geo=geometric mean, unkwn=unknown mean

The WHO Expert Committee met from March 27-31, 2017 and, based on review of a dossier suggesting inclusion of ivermectin as an anthelmintic in the Essential Medicines List, made the following recommendation:

"...adding ivermectin on the Essential Medicines List under the section intestinal anthelminthic for use against Strongyloides stercoralis and STH. It may be used in combination with albendazole for treatment of soiltransmitted helminthiasis."

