10.1	Monitoring and auditing1	21
10.2	2 Access to data, handling of data and samples (data protection), archiving (place, duration) a	ınd
dest	truction1	22
10.3	Data entered directly in the CRF – definition of source data1	22
10.4	Data and safety monitoring board / data monitoring committee1	22
10.5	5 Study Documents: Translations - Reference language1	23
11.	Dissemination of results and publication1	23
12.	References1	24

Page 92 of 176

III.	Abbrevia	tions
AE		Adverse event
AUC		Area under the curve
CI		Confidence interval
CNER		Comité Nationale d'Ethique de la Recherche
CR		Cure rate
CRF		Case report form
CSRS		Centre Suisse de Recherches Scientifiques en Côte d'Ivoire
DF		Dose-finding
DPML	,	Direction de la Pharmacie, du Médicament et des Laboratoires
EKNZ		Ethikkomission Nordwest- und Zentralschweiz
EML		Essential medicine list
EPG		Eggs per gram
ERR		Egg reduction rate
GCP		Good clinical practice
GEE		Generalized estimating equation
Hb		Hemoglobin
ICH		International council for harmonization of technical requirements for pharmaceuticals for human use
IEC		Independent ethics committee
LC-MS	S/MS	Liquid chromatography tandem mass spectrometry
MDA		Mass drug administration
MIC		Minimal inhibitory concentration
MUAC	2	Mid-upper arm circumference
PC		Preventive chemotherapy
PCR		Polymerase chain reaction
PI		Principal investigator
РК		Pharmacokinetic
PK/PD)	Pharmacokinetic/pharmacodynamic
RDT		Rapid diagnostic test
SAE		Serious adverse event
SOP		Standard operating procedure
STH		Soil-transmitted helminth
Swiss 7	ГРН	Swiss Tropical and Public Health Institute
SUSAI	R	Suspected unexpected serious adverse reaction
WHO		World Health Organization

Page 93 of 176

IV. Synopsis

Sponsor/Sponsor- Investigator	[name]. [name]				
Study Title	Efficacy and safety of ivermectin and albendazole co-administration in school- aged children and adults infected with Trichuris trichiura : a multi-country randomized controlled trial				
Short title	Efficacy and safety of IVM/ALB co-administration				
Protocol Number, Date and Version	1, 12.06.2018, v1.01				
Trial registration	Has been registered on ClinicalTrials.gov (reference: NCT 03527732)				
Clinical phase	Phase 3 trial				
Sample size	1960 (600 participants in each of 3 settings for the parallel group trial including 160 participants for the dose-finding (DF) study)				
Indication	Trichuris trichiura infection (eggs in stool)				

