5.2 Inclusion criteria

- 1. Written informed consent signed by either the participant him/herself (≥18 years of age) or by parents and/or caregivers for children/adolescents; and oral assent by child/adolescent (aged 6–17 years).
- 2. Agree to comply with study procedures, including provision of two stool samples at the beginning (baseline) and on three follow-up assessments (approximately 3 weeks, 6 months, and 12 months later).
- 3. Aged ≥ 6 to ≤ 60 years.
- 4. At least two slides of the quadruple Kato-Katz thick smears positive for *T. trichiura* and infection intensities of at least 100 EPG.

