7.3 Description of statistical methods

The primary available case analysis will include all participants with primary end point data. In addition, an intention-to-treat analysis will be conducted considering all participants with missing endpoint data as treatment failure or all as treatment success to ensure that the results are not sensitive to potential loss to follow-up bias. CRs will be calculated as the percentage of egg-positive (larvae-positive for *S. stercoralis*) children at baseline who become egg-negative (larvae-negative) after treatment. EPG will be assessed by adding up the egg counts from the quadruplicate Kato-Katz thick smears and multiplying this number by a factor of six. For *S. stercoralis* infection no further quantification of larvae in stool will be done. The ERR of STH infection will be calculated as:

$$ERR = 1 - \frac{\frac{1}{n}e^{\sum \log(EPG_{follow} - up + 1)} - 1}{\frac{1}{n}e^{\sum \log(EPG_{baseline} + 1)} - 1}$$

In the primary model we estimate the difference among CRs by using unadjusted logistic regressions. In a subsequent analysis an adjusted logistic regression (adjustment for age, sex, and weight) will be performed.

Geometric mean egg counts will be calculated for the different treatment arms before and after treatment to assess the corresponding ERRs. Bootstrap resampling method with 5,000 replicates will be used to calculate 95% confidence intervals (CIs) for ERRs and the difference between the ERRs.

Results from the stool RDT for fecal occult blood will be categorized as negative, trace and positive. For calprotectin, individuals with levels exceeding 50 μ g/g will be considered as positive and concentrations be classified into low (51–149 μ g/g), medium (150–299 μ g/g) and high (\geq 300 μ g/g) intensity [16].

Anthropometric measurements such as height and weight of school-aged children will be translated into weightand height-related z-scores using readily available Stata macros calculating growth indicators for children 5-19 years [34]. Body mass index and indicators for muscle and fat tissue such as MUAC and skinfold thickness will serve as additional indicators of nutritional status for adults and will further be classified using a percentiles approach to compare within populations [35].

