- 33. ICH Expert Working Group: ICH harmonised tripartite guideline. Clinical safety data management: definitions and standards for expedited reporting E2A. International conference on harmonisation of technical requirements for registration of pharmaceuticals for human use; 1994.
- 34. Duggan MB: Anthropometry as a tool for measuring malnutrition: impact of the new WHO growth standards and reference. *Ann Trop Paediatr* 2010, **30**(1):1-17.
- 35. Wang Y, Chen H: Use of Percentiles and Z-Scores in Anthropometry. In: *Handbook of Anthropometry*. Edited by Preedy V. New York: Springer; 2012: 29-48.

Page 163 of 176

7. Statistical Analysis Plan (SAP)

Clinical trial protocol title:	Efficacy and safety of ivermectin and albendazole co-administration in school-aged children and adults infected with Trichuris trichiura : a multi-country randomized controlled trial
Principal Investigator	[name]
ClinicalTrials.gov identifier	03527732
Author	[name]
Version/Date	v1.0/14.9.2020

Page 164 of 176

Contents

Signatures	
Introduction	
Study Objectives and Endpoints	
Study Objectives	
Primary Objective	167
Secondary Objectives	
Study Endpoints	
Primary	
Secondary	
Statistical Hypotheses	
Study Design	
Planned Analyses	169
Interim Analyses	
Final Analysis	
Sample size consideration	
Populations for analysis	
Subgroup analyses	
Data handling conventions and missing data	
Protocol deviations	170
Demographics and other baseline characteristics	171
Efficacy analysis	171
Safety analysis	

Page 165 of 176

Signatures

The following persons have read and agreed on the SAP:

[name]

Trial Statistician

Date of signature 14.9.2020

[name]

Principal investigator

Date of signature 14.9.2020

[name]

Introduction

This Statistical Analysis Plan (SAP) is based on the current trial protocols versions v1.01_19.09.2018 (Lao PDR), v1.03_22.11.2018 (Côte d'Ivoire) and v1.01_13.2.18_(Zanzibar).

Where statistical methods differ substantially between this SAP and the protocol, the differences will be identified in the SAP.

This SAP describes the datasets and the statistical methods to be used for the reporting and analysis of all data collected 3 weeks after treatment in **three randomized controlled trials**. If a future protocol amendment necessitates a substantial change to the statistical analysis of the trial data, this SAP will be amended accordingly.

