Available case population: All participants randomized, excl. those who entered the study even though they did not satisfy the entry criterion 'positive at baseline' with at least one non-missing endpoint data.

Per protocol population: All participants who meet all inclusion and exclusion criteria, have no major protocol deviations and received the correct treatment.

Intention to treat population: All participants randomized, excl. those who entered the study even though they did not satisfy the entry criterion 'positive at baseline'

Safety population: All subjects who received at least one dose of treatment with at least one non-missing safety endpoint with no major protocol deviations.

Efficacy endpoints will be analysed using the available case population according to the ITT principles. The primary analysis will be confirmed using the per-protocol population. Safety endpoints will be analysed using the safety population as treated.

Subgroup analyses

The following pre-specified sub group analyses will be conducted:

- by age category (6-12 years vs. 13+ years)
- by baseline infection intensity (light vs moderate & heavy)

For sub group analyses the data from all trials will be pooled to ensure sufficient power.

Data handling conventions and missing data

All subjects who withdraw prematurely from the study or study drug will be included in the statistical analyses. Experience from previous trials indicated that the proportion of missing data is usually below 10%; therefore, no imputation of missing data is planned. In case the proportion of missing data will be considerably higher than expected the primary analysis using the available case population will be complemented by an analysis using the

Page 170 of 176

intention-to-treat population. For this purpose missing data will be imputed by multiple imputations as implemented in R's 'mi' package.

Protocol deviations

Before closing the database, data listings will be reviewed to identify any significant deviations and determine whether the data should be excluded from any analysis populations.

Protocol deviations leading to exclusion from all analyses populations

• Participants who were negative for *T. trichuria* infection at baseline.

Major protocol deviations include subjects who:

- Entered the study even though they did not satisfy other entry criteria.
- Met the criteria for withdrawal from the study but were not withdrawn.

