- Received no treatment, the wrong treatment or incorrect dose.
- Received an excluded concomitant therapy.

Minor protocol deviations include subjects who:

- Provided fewer stool samples than specified in the protocol
- Provided stool samples later than specified in the protocol (measurements taken outside the allowable windows given in the protocol)
- Vomiting within 1-hour post-dosing without re-treatment.

Participants with major protocol deviations will be excluded from the per-protocol population. Minor protocol deviations will remain in all analysis populations.

Page 171 of 176

Demographics and other baseline characteristics

Baseline characteristics will be calculated and presented as outlined below

	Pemb	a Island	Côte d	'Ivoire	Lao PDR		
Characteristics	ALB (n=xxx)	IVM-ALB (n=xxx)	ALB (n=xxx)	IVM- ALB (n=xxx)	ALB (n=xxx)	IVM- ALB (n=xxx)	
Age, 6-12							
Age, 13-24yrs							
Age, 25 years and above							
Sex, n (%)							
Females							
Males							
Weight, kg							
Height, cm							
T. trichiura infection							
Geometric mean EPG							
Infection intensity ^a , n (%)							
Light							
Moderate							
Heavy							
A. lumbricoides infection							
Infected, n (%)							
Geometric mean EPG							
Infection intensity ^b , n (%)							
Light							
Moderate							
Неаvy							
Hookworm infection							
Infected, no. (%)							
Geometric mean EPG							
Infection intensity ^c , n (%)							
Light							
Moderate							
Неаvy							
S. stercoralis infection ^d							
Infected, n (%)							

^a *T. trichiura* infection intensity classified according to mean eggs per gram of stool (EPG) into: light=1-999 EPG, moderate=1000-9999 EPG and heavy=≥10000 EPG

^b A. lumbricoides infection intensity classified according to mean eggs per gram of stool (EPG) into: light=1-4999 EPG, moderate=5000-49999 EPG and heavy=≥50000 EPG

^c Hookworm infection intensity classified according to mean eggs per gram of stool (EPG) into: light=1-1999 EPG, moderate=2000-3999 EPG and heavy=>4000 EPG

^d Baermann technique to detect *S. stercoralis* infection was only applied to stool samples collected in Lao PDR

Page 172 of 176

In the unadjusted analysis the differences in cure rates will be assessed using a Melded Binomial Confidence Intervals and Tests with mid-p correction as implemented in the 'exact2x2' package.

library(exact2x2)
binomMeld.test(... , # insert n[pos] and n[total]
parmtype = "difference", conf.level = 0.95, conf.int = TRUE,

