alternative = "two.sided", midp = T)

This analysis has been chosen because most biomedical journals prefer the absolute difference over the relative difference. However, adjustment for confounder or effect modifier is not possible; therefore, the adjusted analysis will use standard logistic regression.

Egg reduction rates (geometric mean based) will be calculated using the following formula

$$ERR = 1 - \frac{\frac{1}{n}e^{\sum \log(EPG_{follow} - up + 1)}}{\frac{1}{n}e^{\sum \log(EPG_{baseline} + 1)} - 1}$$

Differences in geometric mean based ERR will be analysed via bootstrap resampling using the following code

}

library(boot) difgm <- boot(data = d, statistic = diffgm, R = 2000, strata = d\$arm)

The arithmetic based ERR will be estimated in the same way.

If the sample size of study participants infected with hookworm, Ascaris lumbricoides and *Strongyloides stercoralis* is considered sufficiently large, efficacy against these parasites will be assessed in the same way. If the number of participants will be below 100 per arm the trial arms will only be compared descriptively.

Page 173 of 176

Efficacy results and estimates will be presented as outlined below

		Pemba Is	land	Côte d'Iv	oire	Lao PDR		Total		
Variab	le	ALB (n=xxx)	IVM- ALB (n=xxx)	ALB (n=xxx)	IVM- ALB (n=xxx)	ALB (n=xxx)	IVM- ALB (n=xxx)	ALB (n=xxx)	IVM- ALB (n=xxx)	
T. trich	iura									
No. of p	participants positive	for								
infectio	n Defere									
	treatment									
	After treatment									
Cure ra	te. % (95% CI)									
No. of p	participants cured n	(%)								
1	From light									
	From moderate									
	infection									
	From heavy									
Carrier	infection									
Geomet	tric mean EPG									
	Before									
	After treatment									
GMEg	g_reduction rate									
% (95%	CI)									
Arithme	etic mean EPG									
	Before									
	treatment									
	After treatment									
AM Eg	g-reduction rate,									
% (95%) A lumb	o CI) bricoid e s									
N partic	cinants positive									
T partic	Before									
	treatment									
	After treatment									
Cure ra	te, %									
N partic	cipants cured (%)									
1	From light									
	infection									
	From moderate									
	infection									
	From heavy									
Geomet	tric mean EPG									
	Before									
	treatment									
	After treatment									
Egg-red	luction rate, %									
Hookw	orm									
N partic	cipants positive	1								
	i 1			1		1		1		

Page 174 of 176

	Before					

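### The SAP's geometric-mean egg reduction rate subtracts 1 from the baseline term but not from the follow-up term, so each arm's ERR comes out too low

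*Combined protocol and SAP*

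**What the plan says.** The SAP's efficacy section defines the geometric-mean ERR as "ERR = 1 - \frac{\frac{1}{n}e^{\sum \log(EPG_{follow} - up + 1)}}{\frac{1}{n}e^{\sum \log(EPG_{baseline} + 1)} - 1". The Pemba protocol, section 7.3, prints the same expression. Section 7.3 of the Laos, Côte d'Ivoire and Swiss (EKNZ) protocols instead prints "ERR = 1 - \frac{\frac{1}{n}e^{\sum \log(EPG_{follow} - up + 1)} - 1}{\frac{1}{n}e^{\sum \log(EPG_{baseline} + 1)} - 1". The only difference is the `- 1` after the follow-up term.

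The SAP's Introduction states that the plan is "based on the current trial protocols versions v1.01_19.09.2018 (Lao PDR"), together with Côte d'Ivoire v1.03 of 22.11.2018 and Zanzibar v1.01 of 13.2.18. It undertakes to point out substantial departures from the protocols and points out none for the ERR. The SAP therefore agrees with one of its base protocols (Pemba) and disagrees with Laos and with the Côte d'Ivoire text as printed. The synopsis of that Côte d'Ivoire text is headed "1, 12.06.2018, v1.01", which is not the version the SAP cites.

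**The concern.** The `+1` inside the log allows for zero egg counts. After exponentiating the mean log, 1 has to come off again to return to eggs per gram. Doing this on one side of a ratio only has no rationale, and the SAP offers none.

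What is at stake is the reported size of a secondary endpoint:

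- Each arm's ERR is biased downwards.
- The SAP's results table sets geometric mean EPG before and after treatment beside the ERR. If those means are back-transformed, a reader dividing one by the other will not get the printed ERR.
- The same method is carried over to *A. lumbricoides* and hookworm, for which there is no minimum egg count at entry.

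**Working it through.** **Reading.** Every copy of the formula shows 1/n outside the exponential. Taken literally, each term would be a product of all the (EPG + 1) values divided by n, which is not a geometric mean. The SAP calls the measure geometric mean based, so 1/n is read inside the exponent.

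**Notation.** Let b and f be the back-transformed geometric means at baseline and follow-up, i.e. `exp(mean log(EPG+1)) - 1`.

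- `- 1` in both terms: `ERR = 1 - f/b`
- SAP form: `ERR = 1 - (f+1)/b`
- Difference: `1/b`, or `100/b` percentage points

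**Boundary cases.** If everyone is cured (f = 0), the SAP form gives 1 - 1/b instead of 100%. If nothing changes (f = b), it gives -1/b instead of 0. The form with both subtractions gives 100% and 0.

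**Size for *T. trichiura*.** Entry requires "infection intensities of at least 100 EPG". EPG is six times the summed count, so the lowest eligible value is 6 × 17 = 102. The means 127 and 489 come from Table 2 of the protocols' background section.

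| b | Loss = 100/b (points) | All-cured ceiling (%) |
|---|---|---|
| 102 | 0.98 | 99.02 |
| 127 | 0.79 | 99.21 |
| 489 | 0.20 | 99.80 |

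The floor of 102 is not strict in the available case population, which drops only participants negative at baseline. Major deviations include those who "Entered the study even though they did not satisfy other entry criteria", and the stated consequence is that "Participants with major protocol deviations will be excluded from the per-protocol population".

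**Arm difference.** The bias is 100 × |1/b1 - 1/b2|. It is 0 with equal baselines. With assumed imbalances it is 0.02 points for 489 against 440 and 0.15 points for 102 against 120.

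**Other species.** The documents give no baseline geometric means. At an assumed mean of 50 the loss is 100/50 = 2 points. The background section cites "CRs >78% and ERRs >99.5"% for the combination against *A. lumbricoides*. Since 100 - 100/200 = 99.5, the SAP form cannot exceed 99.5% unless the baseline mean is above 200 EPG, even with every participant cured.

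**Check against Table 2.** Table 2 holds the documents' only worked geometric-mean ERRs, and it does not say whether 1 had already been subtracted from its means.

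| Before/after | Reported (%) | If back-transformed: both `- 1` | If back-transformed: SAP form | If GM of EPG+1: both `- 1` | If GM of EPG+1: SAP form |
|---|---|---|---|---|---|
| 489/27 | 94.5 | 94.48 | 94.27 | 94.67 | 94.47 |
| 127/11 | 91.3 | 91.34 | 90.55 | 92.06 | 91.27 |
| 550.0/1.9 | 99.7 | 99.65 | 99.47 | 99.84 | 99.65 |

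The first pair of columns uses 1 - f/b and 1 - (f+1)/b. The second uses 1 - (f-1)/(b-1) and 1 - f/(b-1). Each formula reproduces all three reported values under one reading and none under the other, so Table 2 does not settle the point.

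**The case against.** **The missing `- 1` may be a PDF-reading artefact.** The equation is visibly damaged: part of the follow-up subscript has come loose, and 1/n sits outside the exponential throughout. The SAP and Pemba strings are identical, so one may have been pasted from the other, and they are not two independent witnesses. This stands as a reason to check the source file. Still, the term survives in all five denominators and in three numerators, which makes a slip shared by the two texts more likely than extraction loss.

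**If 1/n is silently repaired, the `- 1` could be repaired with equal charity.** The two cases differ. The SAP's own description forces the 1/n reading, whereas nothing in it tells an analyst to subtract 1 at follow-up.

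**The code may be right.** The body of `diffgm` is not visible, so whether reported results would be affected is unknown. That stands, but correct code would then contradict the written formula.

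**The version evidence is mixed.** The printed Laos synopsis is dated 13.06.2018, earlier than the 19.09.2018 the SAP cites, and Pemba, which agrees with the SAP, is the only printed base protocol whose date and version both match. However, the Laos body already contains the microbiome sampling and the 15 kg criterion that the change log dates to 19.09.2018, so it is a fair comparator. Côte d'Ivoire is the weaker comparator.

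**The effect is negligible.** For *T. trichiura* this is largely true, above all between arms, and the documents set no ERR success threshold. The loss in points depends only on the baseline mean, not on the ERR. The figures for other species rest on assumed or unknown baselines, and below 100 participants per arm those comparisons are descriptive only.

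**Conclusion.** The concern holds: the SAP formula is wrong as written. It understates each arm's geometric-mean ERR by 100/b points, which for *T. trichiura* is about 1 point or less at eligible baselines and 0.20 points at a mean of 489. The bias in the arm difference is zero with equal baselines and 0.02 to 0.15 points under the imbalances assumed above. It could be larger within arms for *A. lumbricoides* or hookworm if baseline means are low, but the documents give no figure for this. The primary endpoint and the sample size are untouched, and the severity is minor.

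Confidence is medium. The conclusion assumes that 1/n belongs inside the exponent and that the source PDF really lacks the `- 1`. Any effect on reported results also depends on `diffgm` following the printed formula.

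**What to change.** In the SAP, replace the formula with

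`ERR = 1 - [exp((1/n) × Σ log(EPG_followup + 1)) - 1] / [exp((1/n) × Σ log(EPG_baseline + 1)) - 1]`

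Check the missing `- 1` and the position of 1/n against the source PDF, and confirm that `diffgm` computes this expression. The follow-up terms in the Laos, Côte d'Ivoire and Swiss protocols need no change.

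The cost is one SAP line and a short code check. Correcting the Pemba text as well would be a protocol modification, which under its section 8.1 goes to the ethics committee. A sentence in the SAP stating that its formula supersedes the Pemba one would be a lighter route.

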This important milestone paves the way for further, standardized trials to evaluate the efficacy of this combination among school-aged children in a range of epidemiological settings. In addition, the combination should be evaluated among adults, as there is growing interest in broadening deworming to include adults in order to move from morbidity control toward interruption of transmission [13, 14].

In the proposed work, three trials are planned across a range of transmission settings, including Côte d'Ivoire, Lao PDR, and Pemba (Tanzania). Follow-up will be conducted at 1, 6, and 12 months to inform treatment frequency. Results from these trials will inform decisions on how the combination could be introduced into

Page 143 of 176

existing mass drug administration (MDA) programs and therefore provide a valuable adjunct tool for interrupting STH transmission.

3. Trial objective and purpose

The overall goal of the study is to assess the efficacy and safety of co-administered albendazole and ivermectin versus albendazole monotherapy (standard of care) against *T. trichiura* infections in children and adults (6-60 years) in different transmission settings and geographies.

We hypothesize that albendazole-ivermectin has a higher efficacy against *T. trichiura* infections than albendazole alone, and hence, the efficacy against all three STH species (*A. lumbricoides*, *T. trichiura*, and hookworm) and *Strongyloides stercoralis* will be increased.

The **primary objective** of the trial is to comparatively assess the efficacy in terms of CR against *T. trichiura* infections among school-aged children and adults from three different epidemiological settings and monitored over a 12-month period of the following two oral treatment regimens:

- Albendazole/ivermectin combination
- Albendazole monotherapy

The secondary objectives of the trial are:

- a) To evaluate the safety and tolerability of the treatment regimens
- b) To compare the ERRs of the treatment regimens against *T. trichiura*
- c) To determine the CRs and ERRs of the drugs in study participants (6-60 years) infected with hookworm, *A. lumbricoides* and *S. stercoralis*
- d) To investigate potential extended effects on follow-up helminth prevalences (6 and 12 months post-treatment) of the two treatment regimens (as assessed among participants with cleared infection on days 21 and 180)

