7.2 Justification of number of trial subjects

Based on available summarized efficacy measures from a recent review [1] and the published literature, we assume that the CR of albendazole against *T. trichiura* is 30% compared to 50% in the albendazole-ivermectin treatment regimen. To detect a difference with 90% power at a two-sided 5% significance level, we require 121 participants per study arm and 143 to account for potential loss to follow-up of 15%. We further assume the same treatment efficacy in the mid-term treatment and a 6-months reinfection risk of 10%. Consequently we expect a proportion of negative patients after 12 months of 44% in the albendazole arm and of 65% in the albendazole-ivermectin arm resulting in a required sample size of 111 participants per arm. To account for a loss to follow-up of 30% after 6 months and 40% at final assessment (12 months) we aim to recruit 300 participants in each treatment group (600 in total) in each country.

Subgroup analysis will be conducted stratifying the study population by age category (school-aged and adults). For the subgroup analysis we will pool the data from all 3 countries to ensure sufficient statistical power.

Page 155 of 176

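### The SAP gives no measure of uncertainty for co-infection arm comparisons below 100 participants per arm, and no reason for that cut-off, although its planned cure-rate interval works at smaller numbers

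*Combined protocol and SAP*

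**What the plan says.** In its Efficacy analysis section the SAP covers hookworm, *A. lumbricoides* and *S. stercoralis* after *T. trichiura*. If numbers are judged large enough, "efficacy against these parasites will be assessed in the same way". The next sentence sets the limit: "If the number of participants will be below 100 per arm the trial arms will only be compared descriptively". No reason is given for 100. The SAP does not say whether the count is per country or across countries, or whether it is taken at enrolment or at follow-up.

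For cure rates, the method that would otherwise apply is "Melded Binomial Confidence Intervals and Tests with mid-p correction as implemented in the 'exact2x2' package", run two-sided with mid-p switched on. Egg reduction rates are compared by bootstrap. *S. stercoralis* is recorded only as positive or negative, so for this parasite only the cure-rate comparison arises.

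The results table attaches a 95% CI to the *T. trichiura* cure rate and egg reduction rates. It attaches none to any row for the three co-infections.

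Footnote d of the SAP's baseline table says: "Baermann technique to detect *S. stercoralis* infection was only applied to stool samples collected in Lao PDR". The Lao protocol, section 3, expects that "hence, the efficacy against all three STH species (*A. lumbricoides*, *T. trichiura*, and hookworm) and *Strongyloides stercoralis* will be increased". The SAP lists the *S. stercoralis* cure rate as a secondary endpoint, but its only statistical hypothesis concerns *T. trichiura*.

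**The concern.** A minimum count for inference makes sense when the method breaks down in small samples. The melded binomial mid-p interval was built for small samples, so the cut-off does not follow from the method. Below it, readers get two cure rates with no planned statement of how far apart the true rates could be.

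*S. stercoralis* is the most exposed. It comes from one country, so the table's Total column adds nobody. Pooling is promised elsewhere in the SAP ("For sub group analyses the data from all trials will be pooled to ensure sufficient power"), but that sentence concerns the age and infection-intensity subgroups. The bootstrap, which could justify a minimum for the other two parasites, is not used for it. At stake is a randomised comparison on a listed secondary endpoint for which the Lao protocol states a direction.

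**Working it through.** **1. The plan's own sample size.** Lao protocol section 7.2 sets the terms: "To detect a difference with 90% power at a two-sided 5% significance level", with cure rates of 30% and 50%.

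n = (1.960 + 1.282)² × (0.3×0.7 + 0.5×0.5) / 0.2² = 120.8, so 121 per arm. With 15% loss: 121/0.85 = 142.4, so 143. Both stated figures reproduce.

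**2. Co-infected share needed for 100 per arm in Laos.** The protocol aims to recruit 300 per arm; the SAP anticipates 143.

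- 300 per arm: 100/300 = 33%
- 300 less 15% loss: 100/255 = 39%
- 143 per arm: 100/143 = 70%
- 143 less 15% loss: 100/121.55 = 82%

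**3. Chance that both arms reach 100.** This is the squared binomial probability P(X ≥ 100) with N per arm and co-infected share p. The documents give no p, so a range is shown.

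| p | N = 300 | N = 255 | N = 143 |
|---|---|---|---|
| 20% | about 0 | about 0 | about 0 |
| 30% | 1.4% | about 0 | about 0 |
| 35% | 56% | 0.8% | about 0 |
| 40% | 98.5% | 39% | about 0 |
| 50% | >99.9% | >99.9% | about 0 |

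**4. Does the method hold below 100?** All outcome tables with equal arms were enumerated and rejected at two-sided p ≤ 0.05. The maximum type I error of the melded mid-p test was 0.042 at 10 per arm, 0.050 at 20, 0.055 at 30, 0.057 at 50 and 0.056 at 100. The closely related conditional mid-p test gives 0.052 at 30. The small excess over 0.05 is therefore as large at the cut-off as below it.

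**5. Power below the cut-off.** Melded mid-p test, same enumeration. The documents give no *S. stercoralis* cure rate, so every pair is an assumption.

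| Cure rates | 10 per arm | 20 | 30 | 50 |
|---|---|---|---|---|
| 30% vs 50% | 13% | 22% | 35% | 55% |
| 30% vs 60% | 25% | 45% | 66% | 88% |
| 60% vs 90% | 29% | 61% | 80% | 95% |
| 50% vs 90% | 47% | 82% | 95% | >99% |

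The conditional mid-p test gives 94% for 50% vs 90% at 30 per arm. For 30% vs 50%, mid-p power reaches 83% at 100 per arm.

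**The case against.** The best defence is that restricting small, unpowered secondary comparisons to description is a legitimate pre-specified choice. The SAP words the co-infection objective as determining cure and egg reduction rates, and the Lao protocol's statement on *S. stercoralis* is an expectation derived from *T. trichiura*. For the trial's planning effect, 30% vs 50%, 100 per arm is also about where power becomes acceptable (83%). An unexplained threshold need not be arbitrary, and a minimum count is reasonable for the bootstrap. All of this stands. It argues against calling the rule an error, but it does not explain why an available interval is withheld.

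Four stronger readings are tempting, and the documents do not support them.

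- **The planned method is exact and valid at any size.** With mid-p it is not strictly exact; type I error slightly exceeds 0.05 from about 30 per arm.
- **The *S. stercoralis* comparison will probably go untested.** That needs a prevalence nobody states. At 40% co-infection with 300 per arm the rule would almost surely be met. At 143 per arm it would not be met at any share up to 50%, so the answer also depends on which enrolment figure applies.
- **The rule discards the comparison.** Counts and cure rates by arm are still tabulated, and a reader could compute an interval. The missing CIs are a gap in the table at any sample size, separate from the 100 rule.
- **The cut-off is also too lax, because power above it is poor for hookworm and *A. lumbricoides*.** That needs combination cure rates that must be assumed. For hookworm, the protocol's background reports 50–66.7% with the combination against 79.5% with albendazole, so an assumed improvement departs from the only figures given. Low power above 100 would also argue for a higher minimum, not for removing it.

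**Conclusion.** The point holds as a limitation of lower severity. The SAP withholds inference for co-infection cure rates below an unexplained 100 per arm and plans no CI for any co-infection, while its chosen interval performs about as well at 30 to 50 per arm as at 100.

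For *S. stercoralis* the consequence depends on unknown prevalence. There would be no measure of uncertainty unless co-infection reaches about 33% of 300 per arm, 39% after 15% loss, or 70% of 143. That may happen; the documents do not make it probable. What would be lost depends on the true effect: at 30 per arm a 40-point difference (50% vs 90%) would usually be shown, and a 20-point difference (30% vs 50%) usually would not. These figures rest on assumed cure rates and equal arm sizes.

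**What to change.** For cure rates, remove the 100-per-arm bar. For each parasite and country, report the arm difference with its melded binomial mid-p 95% CI whatever the number infected, labelled secondary and not powered. Add 95% CIs to the co-infection rows of the results table. A minimum count may stay for the bootstrap comparison of egg reduction rates, with its reason stated.

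The cost is a short wording change, extra table entries and a few more calls of a function already in the plan; no new data are needed. The downside is that some intervals will be wide, which the label should make clear.
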